5.7 Criteria for Taking a Participant Off Study

Participants will be removed from study when any of the following criteria apply:

- Lost to follow-up
- Withdrawal of consent for data submission
- Death

The reason for taking a participant off study, and the date the participant was removed, must be documented in the case report form (CRF). In addition, the study team will ensure Off Treatment/Off Study information is updated in OnCore in accordance with DF/HCC policy REGIST-101.

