11.1.6 Survival and Time to Progression Definitions

Overall Survival: Overall Survival (OS) is defined as the time from randomization (or registration) to death due to any cause, or censored at date last known alive.

Progression-Free Survival: Progression-Free Survival (PFS) is defined as the time from randomization (or registration) to the earlier of progression or death due to any cause. Participants alive without disease progression are censored at date of last disease evaluation.

Time to Progression: Time to Progression (TTP) is defined as the time from randomization (or registration) to progression, or censored at date of last disease evaluation for those without progression reported.

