16.3 Analysis Plan

The primary endpoint is the objective response rate (ORR). We will calculate the frequency and percentage of responses. The point estimate of the ORR with a 9% confidence interval based on the exact binomial distribution will be presented.

With a sample size of 35, if the observed ORR is 30%, we will estimate the 95% confidence interval for the ORR to be 14.8% to 45.2%.

Below is a table for the 95% CIs corresponding to varying observed ORR

	95% CI
15%	3.2% to 26.8%
20%	6.8% to 33.3%
30%	14.8% to 45.2%
40%	23.8% to 56.2%

The secondary endpoints are safety, response rate according to immune-related response criteria, duration of response, progression free survival (PFS), and overall survival (OS) for patients with advanced carcinoid tumors treated with the combination of cabozantinib and nivolumab.

Safety will be assessed by analysis of adverse event (AE) and toxicity data. AE and toxicity data, including laboratory values, will be graded using CTCAE version 5.0. Tabulations of toxicities will be provided by organ system and attribution.

Response rate according to immune-related response criteria will be analyzed using the same method for ORR. Duration of response will be summarized using mean, standard deviation, median, and inter-quartile range.

Progression free survival and overall survival will be defined from time of randomization to time of progression or date of death, respectively. Any patients who have not died by the analysis cut-off date or are lost to follow up will be censored at their last date of contact. Any patient that withdraws consent for follow up will be censored on the date of withdrawal of consent. Kaplan-Meier method will be employed to obtain survival estimates and median survival times will be provided. Greenwood's formula will be used to construct 95% confidence intervals around these estimates.

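### Section 16.3 gives PFS and OS one censoring rule (last contact or consent withdrawal) that conflicts with 11.1.6 and can bias PFS upward for patients contacted after a missed scan

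*Combined protocol and SAP*

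**What the plan says.** Section 16.3 (Analysis Plan) introduces both time-to-event endpoints in one sentence: "Progression free survival and overall survival will be defined from time of randomization to time of progression or date of death, respectively". Two censoring sentences follow. Patients who have not died by the data cut-off or "lost to follow up will be censored at their last date of contact. Any patient that withdraws consent for follow up will be censored on" their withdrawal date. Neither sentence names an endpoint. The Kaplan-Meier, median and Greenwood sentences that come next serve PFS and OS alike, and 16.3 contains no other PFS censoring rule.

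Section 11.1.6 treats the two endpoints separately. PFS runs "to the earlier of progression or death due to any cause", and "Participants alive without disease progression are censored at date of last disease evaluation". OS runs "to death due to any cause, or censored at date last known alive". Section 11.1.5 also censors duration of response at the last disease evaluation, in line with the PFS rule of 11.1.6. No section says which definition takes precedence.

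On follow-up, section 11.1 schedules scans every 8 weeks to week 24 and every 12 weeks after that. Section 5.6 continues them every 12 weeks after protocol therapy ends, until progression or death. Section 10 adds contacts without a scan: visits on Days 1 and 15 of each cycle and safety contact for 100 days after treatment. Section 5.7 states "Participants will be removed from study when any of the following criteria apply" and lists loss to follow-up, withdrawal of consent for data submission, and death. Declining scans is not on that list.

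**The concern.** Last contact is a sound censoring date for OS, because any contact shows whether the patient is alive. It is not sound for PFS, because radiographic progression is seen only on a scan. A patient who stops scans but can still be reached would be counted as progression-free and at risk over a period when progression could not have been detected. That enlarges the Kaplan-Meier denominator without allowing those patients a radiographic event, which pushes the curve up.

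Two analysts, one following 16.3 and the other 11.1.6, could therefore report different PFS from the same data. Under 16.3, the same unscanned responder could also be censored at one date for duration of response and at a later one for PFS. PFS is a named secondary objective (section 1.3.4), and with at most 35 patients a few such cases can be visible in the curve.

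**Working it through.** The documents give no PFS median, event count or rate of missed scans, so there is no figure of the plan's own to reproduce. The check has three parts.

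**1. The two rules side by side**

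| Patient | 16.3 as written | 11.1.6, PFS |
|---|---|---|
| Alive, no progression | last contact | last disease evaluation |
| Lost to follow-up | last contact | last disease evaluation |
| Consent withdrawn | date of withdrawal | last disease evaluation |

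The dates often differ, but a difference alters the Kaplan-Meier estimate only if a progression time falls between them. Progressions are dated at scans. If last contact comes before the next scan is due, the patient has left the risk set under both rules by the next scheduled scan, and the estimate is essentially the same.

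**2. Worked example (assumed data, protocol scan grid)**

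Of 35 patients, 7 stop scans after a progression-free week-8 scan and are contacted to week 52. Of the other 28, progressions at weeks 8, 16, 24, 36, 48 and 60 number 5, 5, 5, 4, 3 and 3, and 3 are censored at week 72.

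- Under 11.1.6 the 7 leave at week 8, so 35 - 5 - 7 = 23 are at risk at week 16. PFS at 24 weeks = (30/35)(18/23)(13/18) = (30/35)(13/23) = 48.4%, so the median is 24 weeks. PFS at 48 weeks = (30/35)(6/23) = 22.4%.
- Under 16.3 the 7 stay to week 52, so 30 are at risk at week 16. PFS at 24 weeks = 20/35 = 57.1%. At 36 weeks it is 16/35 = 45.7%, so the median is 36 weeks. PFS at 48 weeks = 13/35 = 37.1%.

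The gap at 48 weeks is 37.1 - 22.4 = 14.7 points. The case is deliberately severe, since all 7 stop at the first scan. It shows the mechanism and is not an expected size.

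**3. Simulation**

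Each scenario has 200,000 patients, scans at weeks 8, 16, 24 and then every 12 weeks, and progression dated at the next scan. The remaining inputs are assumptions: exponential PFS with true median 26, 39 or 52 weeks; 10%, 20% or 30% of patients stopping scans at a time uniform over weeks 0-52; cut-off at 104 weeks; and contact continuing for 0, 14 or 26 weeks, or to cut-off, after scans stop. The 14 weeks corresponds to the 100-day safety contact (100/7 = 14.3).

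52-week PFS (%), 11.1.6 then 16.3:

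| True median | Stop scans | 14 weeks' contact | Contact to cut-off |
|---|---|---|---|
| 26 wk | 10% | 27.8, 29.0 (+1.2) | 27.9, 31.2 (+3.3) |
| 26 wk | 20% | 27.8, 30.2 (+2.4) | 27.9, 34.5 (+6.6) |
| 26 wk | 30% | 27.7, 31.5 (+3.8) | 27.6, 37.8 (+10.2) |
| 39 wk | 10% | 42.6, 43.7 (+1.1) | 42.6, 45.4 (+2.8) |
| 39 wk | 20% | 42.6, 44.9 (+2.3) | 42.5, 48.2 (+5.7) |
| 39 wk | 30% | 42.5, 46.1 (+3.6) | 42.6, 51.1 (+8.5) |
| 52 wk | 10% | 52.6, 53.6 (+1.0) | 52.7, 55.1 (+2.4) |
| 52 wk | 20% | 52.9, 54.9 (+2.0) | 52.9, 57.7 (+4.8) |
| 52 wk | 30% | 52.8, 56.0 (+3.2) | 52.6, 59.7 (+7.1) |

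- With 26 weeks of further contact the rise is 1.6 to 6.7 points.
- With no further contact the two rules agree to the third decimal.
- Censoring at the last evaluation stays within 0.2 points of the fully scanned curve in every scenario.
- The median moves in 4 of the 27 scenarios with further contact, each time by one 12-week scan interval.

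The simulation treats stopping scans as unrelated to prognosis and counts no deaths after scans stop. Deaths during continued contact would be PFS events under 11.1.6, so counting them as events in both analyses would narrow the gap.

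**The case against.** The strongest reply is that 16.3 was never meant to govern PFS. Its censoring sentence speaks of patients who have not died, which is OS language; read literally for PFS, it would also censor living patients who have already progressed. The endpoint-specific rule is in 11.1.6, and 11.1.5 agrees with it. As an account of what the authors intended, this is persuasive. It does not remove the conflict: the sentence follows directly from a joint definition, is not limited to OS, and leaves the Analysis Plan with no other rule for PFS.

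The second reply is that section 5.6 requires scans every 12 weeks after therapy, so patients who are contacted but not scanned depart from the plan, and no rate is given for them. That stands, and it makes any size conditional. So does the remark that the effect is modest against sampling error: at a 52-week PFS of 52.8%, the standard error with 35 uncensored patients would be about sqrt(0.528 x 0.472 / 35) = 8.4 points.

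Some stronger readings are tempting but unsupported:

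- A reader might infer that every withdrawn, lost or living patient gains up to 12 weeks of progression-free time on schedule. The censoring date may move by that much, but the estimate is essentially unchanged unless a due scan is missed and contact follows it.
- A reader might infer that the excess credit is unlimited. It ends at the analysis cut-off, and the only scheduled post-treatment contact apart from scans runs to 100 days.
- A reader might infer that PFS will be tested against historical data. Section 16.3 plans only Kaplan-Meier estimates, medians and confidence intervals; the sole benchmark, 10% against 30% in section 16.2, is for ORR.

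**Conclusion.** The conflict between 16.3 and 11.1.6 is in the current text and should be resolved. The documents do not show that PFS will be overstated. They show that it can be, if 16.3 is followed for PFS and some patients miss a due scan but are contacted afterwards.

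The size rests on assumptions. With 10-30% of patients stopping scans during year 1, 12-month PFS is about 1 to 4 points higher with 14 weeks of further contact and about 2 to 10 points higher with contact to cut-off. The median is usually unchanged. If contact ends before the next due scan, the effect is essentially nil.

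PFS is descriptive and secondary, and the ORR decision rule is untouched. This is a correction that should be made, not a threat to the primary conclusion.

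**What to change.** In section 16.3, limit the last-contact and withdrawal-date rule to OS. Add one sentence for PFS: patients alive without documented progression, including those lost to follow-up or withdrawn, are censored at the date of the last disease evaluation as in 11.1.6, or at registration if there is none after baseline. If last-contact censoring of PFS is wanted at all, report it only as a sensitivity analysis. Settle this before PFS is analysed, so that the rule is not chosen with the results in view.

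The cost is a short edit to 16.3 and no new data. The downside is that reported PFS may be slightly shorter than under the last-contact rule.

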16.4 Interim Monitoring Plan

If in the first stage there are at least 3 patients with an objective response (ORR), accrual will continue to the second stage where an additional 17 patients will be enrolled.

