NCI Protocol #: NCT04197310

DF/HCC Protocol #: 19-403

TITLE: Phase II trial of cabozantinib in combination with nivolumab for advanced carcinoid tumors

Coordinating Center: Dana-Farber Cancer Institute/ Harvard Cancer Center

Principal Investigator (PI): [name]
Dana-Farber Cancer Institute
[contact]

Other Investigators: [name], MPH
Dana-Farber Cancer Institute
[contact]

[name]
Boston Medical Center
[contact]

Statistician:
[name]
Massachusetts General Hospital
[contact]

Project Manager:
[name]
Dana-Farber Cancer Institute
[contact]

Responsible Research Nurses:
[name]
Dana-Farber Cancer Institute
[contact]

[name]
Dana-Farber Cancer Institute
[contact]

[name]
Dana-Farber Cancer Institute
[contact]

NCI-Supplied Agent(s): N/A

Other Agent(s): Cabozatinib – Exelixis; Nivolumab – Bristol-Myers Squibb

IND #: 144470

IND Sponsor: [name]

Protocol Type / Version # / Version Date: Version #6.0 / 20-May-2022

SCHEMA

Diseases:

Well-differentiated
Neuroendocrine Tumors of
non-pancreatic (i.e,
carcinoid) origin

Treatment:

**Nivolumab intravenously every 2 weeks
AND
Cabozantinib orally daily
28 day cycle**

Stage I: safety run-in (N= 18);

If more than 3 patients
demonstrate response measured
by RECIST 1.1 criteria then,
Stage II: expansion (N= 17)

TABLE OF CONTENTS

1	OBJECTIVES	8
1.1	Study Design	8
1.2	Primary Objective(s)	8
1.3	Secondary Objective(s)	8
1.4	Exploratory Objective(s)	8
2	BACKGROUND	9
2.1	Introduction	9
2.2	Rationale	10
2.3	IND Agent(s)	11
2.4	Correlative Studies Background	11
3	PARTICIPANT SELECTION	13
3.1	Eligibility Criteria	13
3.2	Exclusion Criteria	15
3.3	Inclusion of Women and Minorities	17
4	REGISTRATION	18
4.1	General Guidelines for DF/HCC Institutions	18
4.2	Registration Process for DF/HCC Institutions	18
4.3	General Guidelines for Other Investigative Sites	18
4.4	Registration Process for Other Investigative Sites	18
5	TREATMENT PLAN	19
5.1	Treatment Regimen	19
5.2	Pre-Treatment Criteria	20
5.3	Agent Administration	21
5.4	General Concomitant Medication and Supportive Care Guidelines	21
5.5	Criteria for Taking a Participant Off Protocol Therapy	25
5.6	Duration of Follow Up	27
5.7	Criteria for Taking a Participant Off Study	27
6	DOSING DELAYS/DOSE MODIFICATIONS	27
6.1	Dosing/Delays/Omission/Modification	27
6.2	Dose Levels	28
6.3	Hematologic Toxicities	28
6.4	Diarrhea/Colitis	29
6.5	Hepatobiliary Disorders	30
6.6	Elevated Amylase and/or Lipase	32
6.7	Fatigue, Anorexia and Weight loss Disorders	32

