16 STATISTICAL CONSIDERATIONS

16.1 Study Design/Endpoints

The study intends to examine the clinical efficacy and tolerability of cabozantinib and nivolumab in the treatment of patients with advanced carcinoid. The study includes an interim analysis after 18 patients to assure tolerability and to evaluate response rate of combining cabozantinib and nivolumab. This combination is likely to be well tolerated based on prior studies in patients with breast cancer and renal cell carcinoma, but these data require confirmation in patients with carcinoid tumors. This is a one-arm study without randomization. If objectives of the interim analysis are met then enrollment will be expanded to include 17 additional patients.

16.1.1 Primary endpoint:

The primary efficacy endpoint is the objective response rate (ORR) in patients with advanced carcinoid tumors treated with the combination of cabozantinib and nivolumab. ORR is defined using the RECIST 1.1 criteria as the proportion of subjects with a confirmed CR or a confirmed PR.

16.1.2 Secondary endpoint:

The secondary endpoints are safety, response rate according to immune-related response criteria, duration of response, progression free survival (PFS), and overall survival (OS) for patients with advanced carcinoid tumors treated with the combination of cabozantinib and nivolumab.

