16.2 Sample Size, Accrual Rate and Study Duration

The primary objective of this study is to investigate the safety and tolerability of the combination of cabozantinib and nivolumab. Based on the results of a phase II trial of cabozantinib as monotherapy for patients with advanced carcinoid and pancreatic NET and other trials examining anti-PD-1 agents in patients with other malignancies not selected by PD-L1 status, a true objective response rate (ORR) of 10% or less would not be of clinical interest and represents the null hypothesis of this study. A true rate of 30% would be considered a clinically meaningful level of response. The sample size for this study was chosen to have 95% power to declare the combination effective at this rate with a one-sided Type 1 error of no more than 5%.

Using a Simon's two-stage design, 18 patients will be enrolled in the first stage. If in this first stage there are at least 3 patients with an objective response (ORR), accrual will continue to the second stage where an additional 17 patients will be enrolled. If there are at least 7 patients with an objective response among the total 35 patients, the regimen will be considered worthy of further study.

If the true response rate is 10%, the chance the regimen is declared worthy of further study is less than 5% (exact alpha = 0.047). If the true response rate is 30%, the chance that the regimen is declared worthy of further study is 95%

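### Section 16.1 makes tolerability a condition of expanding after 18 patients, but the operative rules count responses only, and the Schema's response threshold conflicts with Sections 16.2 and 16.4

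*Combined protocol and SAP*

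**What the plan says.** The Schema labels the first stage "Stage I: safety run-in (N= 18". Section 16.1 sets two purposes for the interim: "The study includes an interim analysis after 18 patients to assure tolerability and to evaluate response rate". It then makes expansion conditional: "If objectives of the interim analysis are met then enrollment will be expanded to include 17 additional patients". It expects good tolerability from studies in other tumors, "but these data require confirmation in patients with carcinoid tumors".

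The rules that decide expansion mention response only. Section 16.2 has "If in this first stage there are at least 3 patients with an objective response (ORR), accrual will continue to the second stage", and Section 16.4, which is a single sentence, has "If in the first stage there are at least 3 patients with an objective response (ORR), accrual will continue to the second stage". The Schema's condition begins "If more than 3 patients", which means four or more of 18.

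Section 16.2 gives the operating characteristics of the response rule as "exact alpha = 0.047" and 95% power at a true ORR of 30%, with success defined as 7 or more responses among 35.

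On toxicity, Section 12.2 has the DSMC monitor toxicity and accrual up to four times a year. Section 9.2 plans a safety evaluation after six on-treatment biopsies, prompted by concern about biopsy complications. Sections 16.3 and 16.5 describe adverse event tabulations. Sections 5.5 and 6 govern dose holds and discontinuation for individual patients.

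**The concern.** A go/no-go decision with two stated conditions has a rule for only one of them. Nothing says which events count against tolerability, how many are too many, over what follow-up, or which review must take place before patient 19. Section 12.2 lists DLT information among the material the DSMC may see, but no DLT is defined.

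The two sections can then point in different directions. Suppose 4 of 18 patients respond, enough under the Schema, 16.2 and 16.4, and 9 of 18 permanently lose a drug to toxicity. Section 16.4 says accrual continues. Section 16.1 would allow the sponsor to decline, but offers no way to show whether the tolerability objective was met. The judgement would be made after the data are seen, while the response half is fixed in advance.

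The response half has its own conflict: with exactly 3 responses of 18, Sections 16.2 and 16.4 open stage 2 and the Schema does not.

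**Working it through.** **Inputs.** From 16.2: 18 patients in stage 1, 17 in stage 2, success at 7 or more of 35, null ORR 10%, target ORR 30%. Stage-1 threshold g = 3 (16.2, 16.4) or g = 4 (Schema). The plan gives no acceptable or unacceptable toxicity rate, so every event rate t below is an assumption, shown over 20% to 50%.

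**1. Reproduce the plan's figures.** P(success) = sum over x from g to 18 of P(X1 = x) × P(X2 ≥ 7 − x), with X1 ~ Bin(18, p) and X2 ~ Bin(17, p).

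| Stage-1 threshold | ORR 10% | ORR 30% |
|---|---|---|
| 3 or more (16.2, 16.4) | 0.0474 | 0.9016 |
| 4 or more (Schema) | 0.0335 | 0.8181 |
| Printed in 16.2 | 0.047 | 95% |

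The printed alpha identifies 3 or more as the designed threshold. The printed power matches neither row. Other variants do not reach it either: a threshold of 2 or more gives 0.930, a final cut-off of 6 gives 0.928, and a single stage of 35 gives 0.935.

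**2. Does the response rule screen for toxicity indirectly?** Under 3 or more of 18, stage 2 opens with probability 0.940 at ORR 30%, and the rule contains no toxicity term. Toxicity could lower this by taking patients off therapy before a response is confirmed. In the extreme case where no patient with an event can respond and the others respond at 30%, the per-patient response probability is 0.30 × (1 − t). P(X1 ≥ 3) is then 84.3%, 76.2%, 65.4% and 52.0% at t = 20%, 30%, 40% and 50%. Even then, a 50% event rate leaves stage 2 opening about half the time, so response is a weak proxy for tolerability.

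**3. Size of the example.** For 9 of 18, the exact 95% CI is 26.0% to 74.0%. Applied to 17 further patients: 17 × 0.50 = 8.5 expected events, with 17 × 0.260 = 4.4 and 17 × 0.740 = 12.6 at the CI limits.

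**4. What a numeric limit would do.** Trigger probability is P(T ≥ k), T ~ Bin(18, t). If every trigger became a permanent stop and toxicity were independent of response, power at ORR 30% would be 0.9016 × [1 − P(T ≥ k)].

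| Limit | t = 20% | t = 30% | t = 40% | t = 50% | Power, t = 20% | Power, t = 30% |
|---|---|---|---|---|---|---|
| 8 of 18 | 1.6% | 14.1% | 43.7% | 76.0% | 88.7% | 77.5% |
| 7 of 18 | 5.1% | 27.8% | 62.6% | 88.1% | 85.5% | 65.1% |
| 6 of 18 | 13.3% | 46.6% | 79.1% | 95.2% | 78.2% | 48.2% |

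An added condition can only remove routes to success, so alpha stays at or below the 0.0474 of the 16.2 rule, whatever the dependence between toxicity and response. Relative to the Schema's threshold (0.0335), moving to 3 or more does raise alpha.

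**5. Delay.** Follow-up to patient 18's day 56 is 8 weeks. Adding an assumed 1 to 4 weeks to convene an ad hoc DSMC meeting gives 9 to 12 weeks. Waiting for the next quarterly review could take 8 + 13 = 21 weeks, and longer if reviews are less frequent.

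**The case against.** The strongest reply is that toxicity is already overseen. The DSMC reviews it and takes safety questions to the Overall PI and study team. The sponsor may terminate at any time (Section 15), holds take effect immediately at external sites (Appendix D, 3.1), life-threatening complications go to the Overall PI at once (7.3.1), and Section 6 protects individual patients. With one fixed starting dose and a combination expected to be tolerable, leaving the matter to DSMC judgement is a defensible choice.

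Much of this stands. A reader might infer that the plan has no toxicity review, or that it obliges the sponsor to expand however toxic the regimen proves. The documents support neither: Section 12.2 provides the review, and 16.1 and 15 leave room to decline or stop. Nor do they show that a numeric boundary is the only acceptable answer. Reasonable statisticians could prefer structured DSMC judgement, and the table in the working shows that tight limits are expensive.

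What the reply does not reach is the link to the decision. None of these safeguards states what would satisfy the tolerability objective in 16.1, and none must take place before patient 19. The expectation of good tolerability does not settle it either, because 16.1 says that expectation needs confirming in this population and places the check at this interim.

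**Conclusion.** The point holds as a gap between Section 16.1 and the rules meant to carry it out: tolerability is a stated condition of expansion, and the Schema, 16.2 and 16.4 leave it out. The DSMC review exists but has no stated limit and is not tied to this decision. This rests on the text and on no assumed rate.

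The Schema threshold is a plain inconsistency in a decision figure. Three or more is the better-supported reading because it reproduces the printed alpha. That evidence is partial, since the stated 95% power fits neither threshold; the actual power under 16.2 is 90.2%.

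The limits of 6, 7 and 8 of 18 are illustrations. They assume one common event rate per patient, which requires the same follow-up window for each; the power losses also assume independence from response and that every pause is permanent. The change is worth making, but the existing safeguards mean it is not critical.

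**What to change.** 1. In the Schema, change the stage-1 threshold to 3 or more responses of 18.
2. In the Schema, 16.2 and 16.4, state that stage 2 opens only if at least 3 of 18 patients respond **and** the existing DSMC has reviewed stage-1 toxicity, for example through patient 18's day 56, and found tolerability acceptable.
3. Preferably, have the sponsor fix the event, the per-patient window, the acceptable rate and the limit in advance, and print the operating characteristics. The 8-of-18 limit is one candidate; limits of 7 or 6 catch more toxicity and cost more power. If no numeric limit is adopted, say that the DSMC decides by judgement and that its conclusion is recorded before patient 19.
4. While 16.2 is open, re-derive the stated power.

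No extra patients or procedures are needed, and the committee and adverse event data are already in place. The amendment needs IRB approval and, under Section 14, approval by both drug companies before implementation. The main operational cost is a possible accrual hold of about 9 to 12 weeks from patient 18's first dose, assuming an ad hoc meeting; the added wait falls to zero if the required responses arrive after that review.

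The documents do not give accrual status. If stage 1 is already complete, a limit written now would be post hoc, and the sponsor should instead document how tolerability was judged.
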